This study evaluates the effect of a fractionated carbon dioxide laser on surgical scars of the face and neck over 12 months. Anyone with a surgical scar on the face and neck who has not had laser therapy may be eligible. The visits occur every three months for up to 12 months. Subjects will be randomly assigned to receive two high energy treatments or two low energy treatments. During the study visits, the scars will be photographed pre-treatment and the subject will complete a questionnaire to rate the scar. Three physicians will also evaluate the scar: one as a live assessment and the other two will evaluate the scars after each visit using photographs. Patients will receive their assigned treatment, obtain post-treatment instructions, and a diary to record redness, swelling, pain, itching, or other skin changes after treatment. Patients and raters will be blinded to which therapy level the patient receives until the 9-month visit (Visit #3) at which time patients will be unblinded and offered to have a third high energy treatment if in the high energy treatment group or to have two high energy treatments if in the low energy treatment group.

Study Timeline

The study will occur over 14 months. Our tentative timeline consists of recruitment and screening to occur in November 2016-September 2017. Study visits and data collection would occur between November 2016 and September 2017. Preliminary data analysis and publication of preliminary results would occur between August 2017 and March 2018. Final data analysis and publication would be between October 2018 and January 2019.

Introduction

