Minors are not included due to the Mohs patient population of adults only who have undergone surgical excisions of skin cancers on the head or neck. Although participants are not required to be patients in the Mohs clinic, scars and healing may be significantly different in children, making the data less reliable and difficult to interpret. Any patient who has a condition that the PI assesses may put the subject at significant risk, may confound the study results, or may interfere significantly with the subject's participation in the study will be excluded from the study. Pregnant subjects are not included in the study due to insufficient data on the safety of lasers in pregnant patients.

Subject Discontinuation or Withdrawal from Study Participation

Subject Discontinuation

At any time within the trial, subjects may discontinue participation. Subjects who do not complete the trial will be asked to identify the reason for discontinuation and this information will be documented. If the date that they elect to discontinue from the trial occurs shortly after a treatment (within minutes to 30 days after treatment), patients will be asked to return for a follow-up 3 months to evaluate for any significant adverse events. No treatments will be performed. Only photographs of the scar and rating of the scar by the patient and evaluators will be performed at this visit. Also, collection of the diary will occur at this visit. If subjects discontinue from the trial after 30 days, patients will be followed up via phone for the reason of their discontinuation and asked to return the diary as soon as

possible. In either case, subjects will be given the contact information for the research office in case they have further concerns regarding their participation in the trial.

There are no guidelines or endpoints by which early decisions regarding efficacy or lack of efficacy will be made for this FDA approved device. However, the PI could stop the study early if significant unexpected adverse events occur, or enrollment and retention is not adequate.

Screen Failures

Subjects who do not meet the eligibility criteria will be considered screen failures. Any documentation completed prior to the determination of their status will be placed in one of the containers for shredding in our facility. The reason for the disqualification will be noted and the subject will be included in the count for screened subjects for publication purposes.

Study Device: CO2RE Laser

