
If a patient prefers not to have treatment at this visit, they will be asked to return to clinic for this first treatment within 30 days from the screening and randomization visit. Subjects will return for a second treatment 3 months later. With 10 min allotted for treatment, as well as completing the patient questionnaire (5-7 minutes), assessment of adverse events and updating medications and procedures, along with performing photographs (10 min) and having an evaluation by the blinded evaluator, the entire visit may take up to 30-40 min. The diary entries will take 5 minutes each day. Subjects will return again 3 months following the second treatment and will undergo the follow up photos and assessments. Subjects will be unblinded at the third visit to the treatment received and given three options. One option is to exit from the study. The second option is if the subject received the high energy laser treatments, the subject may elect one additional treatment that day. The third option is subjects with low energy treatments have the option to receive two high energy treatments at this visit and a subsequent visit. Those in the high energy group who receive the third optional high energy treatment will return in 3 months for an exit visit and follow-up assessment of the scar (photos, patient POSAS, and observer POSAS) and exit at visit #4. Those in the low energy group who elect the two high energy treatments will follow up in 3 months after Visit #3 for the final high energy treatment, photos, and assessments (patient POSAS and observer POSAS). After receiving the last optional high energy treatment at Visit #4, patients in this low energy treatment group will return to the clinic in 3 mos for the last study visit where pictures will be obtained, survey assessments of the scar will occur, and the

subject will exit from the study. This allows comparison of all subjects following 2 treatments, and adds further data to the high energy laser treatment group for subjects who cross over.

The subjects' participation may be up to 14 months.

Visit Flowchart

Study Visit #1

The subject will verify information regarding the subject's name and contact information. The subject cannot take part in this study if the subject has a history of prior laser treatment to the face or neck, or if

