This visit occurs 3 months after the subject's second treatment with the following activities:

- The subject will return the diary
- The subject will complete a questionnaire
- o The subject will undergo scar evaluation by the research physician
- The subject will have photographs taken
- The treating investigator will let the subject know which treatment the subject received
- o If the subject received the high energy laser treatment, the following will occur:
 - The subject will be offered the option to receive a third high energy treatment.
 - If the subject accepts treatment today, the subject will return in 3 months for the final follow up visit and to exit the study
- o If the subject declines further treatment, the subject will be exited from the study at this visit.

If the subject received the low energy laser treatment, the following will occur:

- The subject will be offered the option to receive two high energy treatments.
 - o If the subject accepted treatment, the subject will receive one treatment today and return in 3 months for the second treatment (Visit 4); the subject will then be asked to return 3 months later for a follow up final study visit (Visit 5).
- o If the subject declined further treatment, the subject will be exited from the study.

Study Visit #4

If the subject were originally treated with the high energy laser, and elected a third treatment at Visit 3, this visit occurs 3 months after the subject's Visit 3 treatment with the following activities:

- The subject will return the subject's diary
- o The subject will complete a questionnaire
- The subject will undergo scar evaluation by the research physician
- The subject will have photographs taken
- The subject will be exited from the study

If the subject were originally treated with the low energy laser, and elected treatment with the high energy laser, this visit occurs 3 months after the subject's Visit 3 treatment with the following activities:

- o The subject will complete a pre-treatment questionnaire
- The subject will receive the last high energy laser treatment The subject will obtain post-treatment instructions
- The subject will obtain a paper diary to record possible reactions such as redness, swelling, pain, itching or color changes following treatment

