- o If the subject has a history of recurrent fever blisters/cold sores on the lips or face, the subject will be offered a three day prescription for an antiviral medication that the subject can fill at the subject's pharmacy to prevent a recurrence since laser treatments may increase the chance of recurrent episodes. The subject would take one pill every twelve hours the day prior to treatment, on the treatment day, and the first day post-treatment. The subject or the subject's insurance plan must cover the cost of the medication. This may delay the treatment to a later date within 30 days of the screening visit.
- The subject will be asked to return in 3 months for a final follow- up visit

Study Visit #5

This visit occurs 3 months after the subject's last treatment if the subject received the low energy laser treatment followed by the high level laser therapy as a final study visit. The subject will not be offered treatment at this follow up visit. The following will occur:

- The subject will return the subject's diary
- o The subject will complete a questionnaire
- o The subject will undergo scar evaluation by the research physician
- The subject will have photographs taken.

At any time, the subject may choose to not participate in the study. If the date that they elect to discontinue from the trial occurs shortly after a treatment (within minutes to 30 days after treatment), patients will be asked to return for a follow-up 3 months to evaluate for any significant adverse events. No treatments will be performed. Only photographs of the scar and rating of the scar by the patient and evaluators will be performed at this visit. Also, collection of the diary will occur at this visit. If subjects discontinue from the trial after 30 days, patients will be followed up via phone for the reason of their discontinuation and to assess for AE/SAEs and asked to return the diary as soon as possible. In either case, subjects will be given the contact information for the research office in case they have further concerns regarding their participation in the trial.

Unscheduled Visits

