Patients who require evaluation outside of the three month windows +/- two weeks due to a related adverse event will be evaluated by the research team at the earliest convenience. If the nature of the evaluation is in regards to an adverse event/significant adverse event, a severe cutaneous reaction to the laser, or having an unrelated cosmetic procedure involving the study scar during the study, staff will evaluate the patient accordingly, document the event, and report any serious adverse events to the SLU IRB within a 24 hour window.

Completion of Study

At the completion of the study, the data obtained will be reviewed and analyzed with the aid of the Saint Louis University Center for Health Outcomes Research. This data will then be presented in the form of a paper and/or scientific poster. At the completion of the study, the data obtained will be presented in the form of a scientific paper and/or scientific poster.

Methods of Assigning Subjects to Treatment Arms

In terms of randomization, a spreadsheet will be created by the principle investigator with the aid of the research staff to predesignate the treatment assignment. For each patient that comes in, the principle investigator will use that as a guide to dictate the treatment arm assigned for that subject.

Blinding

Other than the investigating physician performing the laser treatment, no one (including the subjects, study coordinators, and the physicians who will be evaluating the response to treatment) will know who is receiving the high energy treatment or the low energy treatment until Visit #3.

Unblinding

At the Visit #3, subjects and the investigating physician performing the treatments will know the type of treatment that the subject in question received.

Concomitant Treatments

Prohibited

Patients will be prohibited from obtaining any additional cosmetic procedures during the study (i.e. dermabrasion, chemical peels) that may interfere with the interpretation of the results of the study.

Permitted

Patients will be permitted to continue using the moisturizers and cleansers that they have been using for the last 6 months. Patients will be allowed to take all oral medication (except isotretinoin) throughout the study.

Benefits and Alternatives

Benefits

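### Subjects who stop more than 30 days after a treatment get no exit scar assessment, so under even dropout most dropouts would lack the Visit 3 outcome; the two phone-call texts also differ on adverse events.

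*Combined protocol and SAP*

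**What the plan says.** The discontinuation rule appears twice in the combined protocol and SAP: under Subject Discontinuation, and again at the end of the Study Visit #5 text.

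- **Stopping early.** Both versions cover a subject who stops "within minutes to 30 days after treatment), patients will be asked to return for a follow-up 3 months to evaluate for any significant adverse events". That return visit involves no treatment: "Only photographs of the scar and rating of the scar by the patient and evaluators will be performed at this visit". The diary is also collected.
- **Stopping later, under Subject Discontinuation.** "If subjects discontinue from the trial after 30 days, patients will be followed up via phone for the reason of their discontinuation". The subject is also asked to send back the diary. No photograph or rating is planned, and adverse events are not named as part of the call.
- **Stopping later, under Study Visit #5.** The same rule, with one addition: "patients will be followed up via phone for the reason of their discontinuation and to assess for AE/SAEs". Again no photograph or rating is planned.

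The blinded schedule has two intervals of equal length. For treatment 1 to treatment 2, Study Procedures states "Subjects will return for a second treatment 3 months later". For treatment 2 to the blinded endpoint, Study Visit #3 states "This visit occurs 3 months after the subject's second treatment with the following activities". The window of plus or minus two weeks is given under Unscheduled Visits.

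Data Analysis and Statistical Considerations names a chi-square test and a Wilcoxon signed rank test between visits. It defines no analysis population and no handling of missing outcomes.

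**The concern.** Study Procedures treats the assessment after two treatments as the point at which all subjects can be compared, so Visit 3 carries the main randomised contrast. The discontinuation rule ends scar measurement for a subject who leaves later than day 30 after a treatment, although the protocol already has a no-treatment visit that could supply it.

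By that stage a subject has had time to judge the result. Leaving could then plausibly be related to how the scar looks, or to reactions that differ between the energy arms. The documents neither show nor exclude this. If it happens, a comparison of those who remain is biased, and data never collected cannot be recovered at analysis. With 50 subjects, and a target of only 10 older scars per arm, a few losses matter.

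The safety side is smaller but real. Tolerability is the secondary objective and the diary runs for 30 days. For a late discontinuer the phone call is therefore the only planned safety contact, and the two versions of the rule disagree on whether it covers adverse events.

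**Working it through.** **No plan figure to reproduce.** The sample size of 50 (Study Population) comes without alpha, power, effect size, SD or dropout rate. The check therefore asks which dropouts the stated rule leaves unmeasured.

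**Inputs from the documents.** Two blinded intervals of 3 months, taken as L = 91 days each; a window of 14 days either way, so 77 to 105 days; a cut-off at day 30 after a treatment; 50 subjects.

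**Assumptions.** Withdrawals before Visit 3 are spread evenly over the two intervals, and everyone asked back attends.

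**Step 1: share with phone contact only.** (L − 30)/L:
- L = 91: 61/91 = 67%
- L = 77: 47/77 = 61%
- L = 105: 75/105 = 71%

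**Step 2: what each dropout would have.** The total time at risk is 2 × 91 = 182 days.

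| Time of stopping | Share of dropouts | Scar data under the rule |
|---|---|---|
| Within 30 days of treatment 1 | 30/182 = 16.5% | Return visit, after one treatment |
| Later, before treatment 2 | 61/182 = 33.5% | Baseline only |
| Within 30 days of treatment 2 | 30/182 = 16.5% | Return visit, equivalent to Visit 3 |
| Later, before Visit 3 | 61/182 = 33.5% | Visit 2 data, nothing after treatment 2 |

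Hence:
- no exit assessment: 122/182 = 67%
- no outcome after two treatments: 152/182 = 83.5%
- no post-baseline scar outcome at all: 61/182 = 33.5%

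The last line relies on scar data being taken at Visit 2. The opening summary says so ("During the study visits, the scars will be photographed pre-treatment and the subject will complete a questionnaire to rate the scar"), the Vectra section has imaging at each visit, and Study Procedures places photographs and a blinded evaluation at the second-treatment visit. The list under Study Visit #2 is shorter and names only a questionnaire.

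**Step 3: vary the timing.** Let f be the share of dropouts within 30 days of a treatment (20% to 80%), and g the share in the first interval (30% to 70%).
- No exit assessment, 1 − f: 20% to 80%
- No post-baseline outcome, g(1 − f): 0.3 × 0.2 = 6% to 0.7 × 0.8 = 56%
- No Visit 3 equivalent, 1 − (1 − g)f: 1 − 0.7 × 0.8 = 44% to 1 − 0.3 × 0.2 = 94%

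**Step 4: counts out of 50, even spread, assumed dropout rates.**

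| Dropout rate (assumed) | Dropouts | No exit assessment | No Visit 3 equivalent | No post-baseline outcome |
|---|---|---|---|---|
| 10% | 5 | 3.4 | 4.2 | 1.7 |
| 20% | 10 | 6.7 | 8.4 | 3.4 |
| 30% | 15 | 10.1 | 12.5 | 5.0 |

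**Step 5: precision, for context only.** For an assumed two-arm comparison of means (two-sided alpha 0.05, 80% power, normal approximation), the detectable difference is (1.96 + 0.84) × √(2/n) SD. This gives 0.79 SD at n = 25 per arm, and 0.89 SD at n = 20 per arm, the number left if all of a 20% dropout is lost. The plan specifies no such test.

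**The case against.** A reader might infer that most dropouts would have no scar outcome. The documents do not support that. Assessments are placed at Visit 2, so about half of the phone-only group should already have a measurement after one treatment. Under even dropout only about one third have nothing after baseline. Subjects who leave after Visit 3 already have the assessment after two treatments.

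A reader might also take it as fact that most dropouts fall after day 30. This is an assumption. If 80% of withdrawals came within 30 days of a treatment, the phone-only share would fall to 20%.

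Nor does the rule itself make dropout depend on outcome; it only fails to recover the data. The plan gives subjects a reason to stay, since further high energy treatment is offered to both arms at Visit 3. The loss of precision is modest and rests on a comparison that the plan does not name.

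On safety, it would go too far to say that late adverse events in discontinuers are missed. The Study Visit #5 text includes them in the call, discontinuers receive the research office's contact details, Reporting of Adverse Events asks subjects to report events, and Reporting Serious Adverse Events covers SAEs to study end and later device-related ones. These provisions narrow the gap. Apart from the call, they depend on the site learning of the event.

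All of this limits the size of the point. It does not supply an exit assessment for late discontinuers, a Visit 3 outcome for most dropouts under even spread, or a missing-data method.

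**Conclusion.** The point holds in a limited form. Neither version of the rule plans an exit scar assessment for subjects who stop more than 30 days after a treatment, and the two versions differ on AE/SAE assessment. Both facts are read directly from the text.

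The size depends on dropout timing, which the documents do not give. The central figures (67% without an exit assessment, 83.5% without the outcome after two treatments, about one third with no post-baseline outcome) rest on even dropout over two 91-day intervals and on Visit 2 scar data being collected. The figure for the outcome after two treatments is the least sensitive in its conclusion: it runs from 44% to 94% over the timings tried.

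Bias in the completers' comparison is possible if leaving depends on result or arm. It is not demonstrated. Confidence is medium. The change is worth making because it is cheap and the loss cannot be repaired later.

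**What to change.** Amend Subject Discontinuation and the matching text under Study Visit #5 so that they state one rule:

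- Keep the existing 3-month return for subjects who stop within 30 days of a treatment. The new visit must not displace it. For those who stop soon after treatment 2, the two fall at the same time and one visit serves both.
- Invite every subject who discontinues before Visit 3, whatever the timing, to the no-treatment assessment already described (photographs, patient and observer POSAS, diary) at the planned Visit 3 date.
- Define that date. The opening summary calls Visit 3 the 9-month visit, while the 3-month intervals place it about 6 months after the first treatment.
- Reconcile the two phone-call texts on AE/SAE assessment.

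In Data Analysis and Statistical Considerations, state that these assessments are analysed in the group to which the subject was randomised, and say how outcomes still missing will be handled.

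The cost is a short amendment and a few extra visits using existing procedures: about 3, 7 or 10 phone-only subjects at 10%, 20% or 30% dropout, plus second visits for those who stopped early after treatment 1. Subjects may decline, so the change reduces the missing data but does not remove it.

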The primary objective is to assess the efficacy of fractionated carbon dioxide laser in improving surgical scars. Objective assessment of the scars will involve the Vectra microtopographic imaging system to measure changes in the length of the scar. The Patient and Observer Scar Assessment Scale (POSAS) is a validated survey that will be utilized for subjective assessments of the vascularity, pigmentation, thickness, pliability, surface area, relief, pain, and pruritus.

The secondary objective will be to evaluate the tolerability of the laser, by assessing the severity and duration of known side effects of laser therapy such as erythema, edema, burning sensation, post-inflammatory pigment changes, infection, scarring, xerosis, pruritus, bronzing, and any other adverse events that arise following treatment. Patients will be given a 30-diary after each treatment to document this information.

Selection and Withdrawal of Study Subjects

Study Population

The study population will consist of 50 adult patients 18 years of age or older with surgical scars located on the head and neck.

Minors are not included due to the Mohs patient population being adults only who have undergone surgical excisions of skin cancers on the head or neck. Although participants are not

required to be patients in the Mohs clinic, scars and healing may be significantly different in children, making the data less reliable and difficult to interpret.

Inclusion and Exclusion Criteria

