This fractionated ablative laser is FDA approved for the revision of surgical scars. Access to this laser may also be obtained outside of the study.

Mechanism of Action

The 10,600 nm carbon dioxide (CO2) laser utilizes high energy at short durations to vaporize intra- and extra-cellular water, resulting in tissue ablation causing a substantial thermal injury to the dermis, reducing the likelihood of additional scarring (Chapas, 2008). The incorporation of fractional photothermolysis, first introduced by Manstein et, al. facilitates a controlled area of dermal injury creating cylindrical microscopic treatment zones (MTZ) of necrosis (Hong Li, 2010, Manstein et al, 2004). Sparing uninvolved normal healthy tissue, each wound is surrounded by healthy cells that can migrate towards the wound, allowing for faster healing by secondary intention (Manstein et al, 2004). The fractionated CO2 laser is selective in that segments of tissue are effected, which translates into decreased recovery time (downtime) for the patient (Bordenorf, 2009). Therefore, by causing selective thermal injury in the skin, the CO2 laser can stimulate collagen production and theoretically improve scar thickness, pliability, and texture.

Dose Regimen

Subjects will be randomized to either a high energy treatment (CO_2RE Mid treatment mode [45-257 mJ] or CO_2RE Deep treatment [30-70 mJ] mode) or a low energy treatment (CO_2RE Light treatment mode [18-74.5 mJ] mode).

Study Device: Canfield Vectra M3 Imaging System

This body imaging is utilized in several clinical trials to capture 3-D photographs of subjects. Subjects will have images and dimensions of their scars measured in a non-invasive manner at each visit using photographs taken with the Canfield Vectra M3 3D Body Imaging System. Detailed step-by-step instructions for executing the images and measuring the scars will be a separate document.

Study Procedures

[figure not shown]

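### The stated mJ ranges do not support the high and low energy labels: Deep (high) lies wholly inside Light (low), and no rule for choosing Mid or Deep is given

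*Combined protocol and SAP*

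**What the plan says.** All references are to the combined protocol and SAP.

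- **Study summary (opening section).** The randomised contrast is named by energy: "Subjects will be randomly assigned to receive two high energy treatments or two low energy treatments".
- **Dose Regimen, under the CO2RE laser.** This is the only place in the supplied text where the arms are given numbers. The high arm: "Subjects will be randomized to either a high energy treatment (CO_2RE Mid treatment mode [45-257 mJ] or CO_2RE Deep treatment [30-70 mJ] mode". The low arm: "a low energy treatment (CO_2RE Light treatment mode [18-74.5 mJ] mode". The section does not say what the mJ figure refers to (per pulse, per spot or per microscopic zone). It gives no spot size, density, fluence or depth for any mode.
- **Methods of Assigning Subjects to Treatment Arms.** "a spreadsheet will be created by the principle investigator with the aid of the research staff to predesignate the treatment assignment". The text describes the spreadsheet as a guide to the arm. It does not say whether the spreadsheet also fixes the mode or setting.
- **Study Objectives.** "The primary objective is to assess the efficacy of fractionated carbon dioxide laser in improving surgical scars". No energy-response objective is stated.
- **Study Procedures and Study Visit #3.** After unblinding, a low-arm subject is offered further laser: "The subject will be offered the option to receive two high energy treatments". High-arm subjects may take a third high energy treatment. Of the resulting data, Study Procedures says: "This allows comparison of all subjects following 2 treatments".
- **Visit descriptions.** Visits 1 to 5 refer only to high or low energy treatment, with no mode or setting.

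**The concern.** The protocol names its randomised contrast by energy, so readers will take a between-arm result as a statement about energy. The ranges printed beside the labels do not order the arms that way. One of the two permitted high modes has a range that is entirely available in the low arm, and its maximum is below the low arm's maximum. Nothing in the supplied text says when Deep rather than Mid is used.

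Interpretation is what is at stake. The Introduction calls the trial placebo-controlled, but no sham or untreated arm is described, so the Light arm is the only concurrent comparator. If the arms differ, the difference could come from mode characteristics other than energy. If they do not, the result could be misread as showing that energy level makes no difference. The same definition carries over to the optional treatments from Visit 3, so the meaning of high energy is equally open there. That is the same gap, not a second one.

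**Working it through.** The plan states no derived figure to reproduce. The check compares the three ranges in Dose Regimen and then searches the rest of the text for something that resolves them.

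**Inputs (mJ, all from Dose Regimen)**
- Light (low arm): 18 to 74.5, width 74.5 − 18 = 56.5
- Deep (high arm): 30 to 70, width 70 − 30 = 40
- Mid (high arm): 45 to 257, width 257 − 45 = 212

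**1. Is Deep inside Light?** This requires Deep minimum ≥ Light minimum and Deep maximum ≤ Light maximum. 30 ≥ 18 and 70 ≤ 74.5, so containment is exact. Deep covers 40/56.5 = 70.8% of the Light range.

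**2. Does Mid overlap Light?** The overlap runs from max(45, 18) = 45 to min(257, 74.5) = 74.5, a width of 29.5. That is 29.5/212 = 13.9% of Mid and 29.5/56.5 = 52.2% of Light. The rest of Mid, (257 − 74.5)/212 = 182.5/212 = 86.1%, lies above the Light maximum.

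**3. High arm as a whole against Light.** Mid and Deep together run from 30 to 257 without a gap. They overlap Light from 30 to 74.5, which is 44.5/56.5 = 78.8% of Light. Only values below 30 mJ (Light) and above 74.5 mJ (Mid) belong to one arm alone.

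**4. Extreme high-minus-low differences for a pair of within-protocol treatments.** These subtractions are meaningful only if mJ is the same quantity in each mode, which is an assumption.

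| Pair | Lowest | Highest |
|---|---|---|
| Deep − Light | 30 − 74.5 = −44.5 | 70 − 18 = +52 |
| Mid − Light | 45 − 74.5 = −29.5 | 257 − 18 = +239 |

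Both rows include values that run against the labels.

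**5. What these numbers do not show.** The percentages are shares of range width, not of treatments. The documents give no distribution of settings and no Mid/Deep split, so no average separation between the arms can be calculated.

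**6. Does other text resolve it?**
- The visit descriptions use only the arm labels.
- The remark in Study Procedures about a deeper scar concerns anaesthetic injection, not laser mode.
- The separate instructions mentioned under the Vectra system cover imaging and scar measurement.
- The randomisation spreadsheet is not shown.
- A figure at the start of Study Procedures, shortly after Dose Regimen, is not reproduced. A rule there cannot be excluded, though the surrounding text does not point to one.

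**The case against.** The strongest reply is that the arms are in fact separated. They use different named modes, Light against Mid or Deep, with none in common. The modes may differ in depth, density or beam pattern, and energy may simply be shorthand for that. The primary objective is laser efficacy, and the only tests named in Data Analysis and Statistical Considerations address change between visits, so no energy conclusion is formally planned. The Study Procedures sentence about comparison after two treatments follows the description of optional treatment. It may mean comparison after two high energy treatments, not the randomised comparison. Most of the Mid range also lies above Light.

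Much of this stands. The contrast by mode is real and randomised, the labels may have a sound basis elsewhere, and the Study Procedures sentence can be read either way, so the point should not depend on it. None of it removes the mismatch. The arms are still named by energy in the summary and in Dose Regimen, the figures given there do not order them by mJ, and Deep is permitted without a stated limit or rule.

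A reader might go further and infer that the two arms receive essentially the same treatment, that the labels are wrong, or that the randomised comparison is invalid. The documents support none of these. Overlapping ranges do not show which settings will be used, and mJ may not be comparable across modes. A reader might also take range midpoints to estimate how far apart the arms will be, but nothing in the documents supports midpoint use.

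**Conclusion.** The point holds as one of labelling and interpretation. It should be corrected, but it does not undermine the randomisation. The containment of Deep in Light and the 29.5 mJ overlap of Mid with Light follow directly from the printed figures and need no assumption. That a high energy treatment can be given at fewer mJ than a low energy one (by up to 44.5 mJ for Deep and 29.5 mJ for Mid) rests on mJ being the same quantity in all three modes, which is not stated. That no separating parameter or Mid/Deep rule exists can be said only of the supplied text, because one figure and the spreadsheet are not shown. On the stated figures, a between-arm difference or null result can be attributed to mode (Mid/Deep versus Light) but not to energy level. How far the arms will differ in practice cannot be determined from the documents.

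**What to change.** 1. Reconcile the Dose Regimen ranges with the arm labels. State what mJ refers to in each mode, what the labels are based on, and how Mid or Deep is chosen within the high arm. The sponsor must settle these passages; no dose, mode or setting is proposed here.
2. Unless an energy parameter that separates the arms is then stated, name and interpret the comparison as Mid/Deep versus Light mode throughout.
3. Report the mode and energy setting used at each treatment by arm, including the optional treatments from Visit 3. Record them at the time if this is not already done, since settings not captured then may be unrecoverable; the site's source documents are not shown, so they may already hold these fields. Keep the report descriptive, because the text does not say that Mid or Deep is randomised within the high arm.

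The cost is a protocol clarification, one descriptive table and possibly one or two fields on the treatment form. The downside is a narrower conclusion, about mode and not energy, if no separating energy parameter can be given.
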